APPENDIX 2: INTERMACS PROFILE/CLASSIFICATION

INTERMACS Profile*	Definition
1	Critical cardiogenic shock describes a patient who is “crashing and burning”, in which a patient has life-threatening hypotension and rapidly escalating inotropic pressor support, with critical organ hypoperfusion often confirmed by worsening acidosis and lactate levels.
2	Progressive decline describes a patient who has been demonstrated “dependent” on inotropic support but nonetheless shows signs of continuing deterioration in nutrition, renal function, fluid retention, or other major status indicator. Patient profile 2 can also describe a patient with refractory volume overload, perhaps with evidence of impaired perfusion, in whom inotropic infusions cannot be maintained due to tachyarrhythmias, clinical ischemia, or other intolerance.
3	Stable but inotrope dependent describes a patient who is clinically stable on mild-moderate doses of intravenous inotropes (or has a temporary circulatory support device) after repeated documentation of failure to wean without symptomatic hypotension, worsening symptoms, or progressive organ dysfunction (usually renal). It is critical to monitor nutrition, renal function, fluid balance, and overall status carefully in order to distinguish between a patient who is truly stable at Patient Profile 3 and a patient who has unappreciated decline rendering this person a Patient Profile 2. This patient may be either at home or in the hospital.
4	Resting symptoms describes a patient who is at home on oral therapy but frequently has symptoms of congestion at rest or with ADL. He or she may have orthopnea, shortness of breath during ADL such as dressing or bathing, gastrointestinal symptoms (abdominal discomfort, nausea, poor appetite), disabling ascites or severe lower extremity edema. This patient should be carefully considered for more intensive management and surveillance programs, by which some may be recognized to have poor compliance that would compromise outcomes with any therapy.
5	Exertion Intolerant describes a patient who is comfortable at rest but unable to engage in any activity, living predominantly within the house or housebound. This patient has no congestive symptoms, but may have chronically elevated volume status, frequently with renal dysfunction, and may be characterized as exercise intolerant.
6	Exertion Limited also describes a patient who is comfortable at rest without evidence of fluid overload, but who is able to do some mild activity. Activities of daily living are comfortable and minor activities outside the home such as visiting friends or going to a restaurant can be performed, but fatigue results within a few minutes of any meaningful physical exertion. This patient has occasional episodes of worsening symptoms and is likely to have had a hospitalization for heart failure within the past year.
7	Advanced NYHA Class 3 describes a patient who is clinically stable with a reasonable level of comfortable activity, despite history of previous decompensation that is not recent. This patient is usually able to walk more than a block. Any decompensation requiring intravenous diuretics or hospitalization within the previous month should make this person a Patient Profile 6 or lower.

*Stevenson, L.W. et al. INTERMACS Profiles of Advanced Heart Failure: The Current Picture, J Heart Lung Transplant. 2009 28(6): 535-541

APPENDIX 3: NYHA CLASSIFICATION

Classification	Definition
I	Cardiac disease without resulting limitations of physical activity. Ordinary physical activity does not cause undue fatigue, palpitations, dyspnea or anginal pain.
II	Cardiac disease resulting in slight limitation of physical activity. Subjects are comfortable at rest. Ordinary physical activity results in fatigue, palpitation, dyspnea or anginal pain.
IIIA	Cardiac disease resulting in marked limitations of physical activity. Subjects are comfortable at rest. Less than ordinary physical activity causes fatigue, palpitation, dyspnea, or anginal pain.
IIIB	Cardiac disease resulting in marked limitations of physical activity. Subjects are comfortable at rest. Mild physical activity causes fatigue, palpitation, dyspnea, or anginal pain.
IV*	Cardiac disease resulting in inability to carry on any physical activity without discomfort. Symptoms of cardiac insufficiency or of the anginal syndrome may be present even at rest. If any physical activity is undertaken, discomfort is increased.

*For all post-enrollment NYHA assessments, any patient who is inotrope dependent will be considered NYHA Class IV.

APPENDIX 4: 6MWT PROTOCOL

SIX-MINUTE HALLWAY WALK TEST INSTRUCTIONS

Purpose

The purpose of the 6-Minute Hallway Walk test (6MWT) is to walk as far as possible for 6-minutes, without running or jogging, as a way of measuring functional status.

Preparing for the test

1. Establish a 30-meter walking course in an enclosed corridor, preferably free of distractions and close to a wall so that if needed, the Subject may rest against it during the test (note: a treadmill is not an acceptable alternate method for this study).
2. Mark the course at 3-meter intervals using a method unnoticeable to the Subject.
3. Place noticeable markers at either end of the 30-meter course to indicate the turnaround points.
4. The distance covered during the preceding walk test will not be revealed to the Subject during the study.
5. A warm up prior to the test should not be performed.

Explaining the test procedure to the Subject

1. Clearly explain to the Subject what is required of him/her using the following instructions verbatim:

THE PURPOSE OF THIS TEST IS TO WALK AS FAR AS POSSIBLE FOR SIX-MINUTES. YOU WILL START FROM THIS POINT AND FOLLOW THE HALLWAY TO THE MARKER AT THE END, THEN TURN AROUND AND WALK BACK. WHEN YOU ARRIVE BACK AT THE STARTING POINT, YOU WILL GO BACK AND FORTH AGAIN. YOU WILL GO BACK AND FORTH AS MANY TIMES AS YOU CAN IN THE SIX-MINUTE PERIOD. IF YOU NEED TO, YOU ARE PERMITTED TO SLOW DOWN, TO STOP, AND TO REST AS NECESSARY. YOU MAY LEAN AGAINST THE WALL WHILE RESTING, BUT RESUME WALKING AS SOON AS YOU ARE ABLE. HOWEVER, THE MOST IMPORTANT THING ABOUT THE TEST IS THAT YOU COVER AS MUCH GROUND AS YOU POSSIBLY CAN DURING THE SIX MINUTES. I WILL KEEP TRACK OF THE NUMBER OF LAPS YOU COMPLETE AND I WILL LET YOU KNOW WHEN THE SIX MINUTES ARE UP. WHEN I SAY STOP, PLEASE STAND RIGHT WHERE YOU ARE.

DO YOU HAVE ANY QUESTIONS ABOUT THE TEST?

PLEASE EXPLAIN TO ME WHAT YOU ARE GOING TO DO.

2. The Subject will re-state the instructions. If the Subject does not seem to understand, repeat the entire instructions.

Conducting the test

1. Position the Subject at the starting line.
2. Repeat the sentence:

THE MOST IMPORTANT THING ABOUT THE TEST IS THAT YOU COVER AS MUCH GROUND AS YOU POSSIBLY CAN DURING THE SIX MINUTES.

ARE YOU READY?

START NOW, OR WHENEVER YOU ARE READY.

3. Start the timer as soon as the Subject takes the first step.
4. During the test, the walking pace of the Subject should not be influenced. The test supervisor must walk behind the Subject – do not walk with, rush up behind, or rush past the Subject.
5. Each time the Subject returns to the starting line, record the lap.
6. While walking, encourage the Subject at one minute intervals with the following phrases:

1 minute: YOU ARE DOING WELL. YOU HAVE 5 MINUTES TO GO.
2 minutes: KEEP UP THE GOOD WORK. YOU HAVE 4 MINUTES TO GO.
3 minutes: YOU ARE DOING WELL. YOU ARE HALFWAY DONE.
4 minutes: KEEP UP THE GOOD WORK. YOU HAVE ONLY 2 MINUTES LEFT.
5 minutes: YOU ARE DOING WELL. YOU HAVE ONLY ONE MINUTE TO GO.

7. The Subject should be spoken to only during the 1-minute encouragements; no response should be made to the Subject's questions about the time and distance elapsed.
 - a. If the Subject is not concentrating on the walking, the Subject can be reminded at a 1-minute mark:

THIS IS A WALKING TEST, TALKING WILL UTILIZE YOUR ENERGY RESERVE AND INTERFERE WITH YOUR PERFORMANCE.

7. When only 15 seconds remain, state:

IN A MOMENT I AM GOING TO TELL YOU TO STOP. WHEN I DO, STOP RIGHT WHERE YOU ARE AND I WILL COME TO YOU.

9. When the timer reads 6-minutes, instruct the Subject to STOP and walk over to him/her. Consider bringing a chair if the Subject appears exhausted. Mark the spot where the Subject stopped.

If the Subject wishes to stop walking during the test

If the Subject is slowing down and expresses that he/she wants to pause, keep the timer running and state:

REMEMBER, IF YOU NEED TO, YOU MAY LEAN AGAINST THE WALL UNTIL YOU CAN CONTINUE WALKING AGAIN.

If the Subject wishes to stop before the 6-minutes are complete and refuses to continue (or you decide that he/she should not continue), provide a chair for the Subject to sit on and discontinue the test. Record the distance completed, the time the test was stopped and the reason for pre-maturely stopping.

Immediately after the test

1. Total the number of completed laps and add the additional distance covered in the final partial lap. Record the distance walked to the nearest meter.
2. Observe the Subject sitting in a chair for at least 10 minutes after the test is completed.

APPENDIX 5: MODIFIED RANKIN SCORE

Score	Definition¹
0	No observed neurological symptoms
1	No significant neurological disability despite symptoms; able to carry out all usual duties and activities
2	Slight neurological disability; unable to carry out all previous activities, but able to look after own affairs without assistance
3	Moderate neurological disability; requiring some help, but able to walk without assistance
4	Moderate severe neurological disability; unable to walk without assistance and unable to attend to own bodily needs without assistance
5	Severe neurological disability; bedridden, incontinent and requiring constant nursing care and attention as a result of a neurological deficit
6	Dead

¹ van Swieten J, Koudstaal P, Visser M, Schouten H, *et al* (1988). "Interobserver agreement for the assessment of handicap in stroke Subjects". *Stroke* **19** (5): 604-607

APPENDIX 6: INTERMACS DEFINITIONS FOR INTENDED USE OF DEVICE

Bridge to recovery - Use of a durable device to allow recovery from chronic cardiac failure (at least 3 months in duration)

Rescue therapy - Use of a durable device to support resolution from an acute event without major previous cardiac dysfunction

Bridge to transplant– This is for a patient ALREADY listed for transplant or listed within 24 hours before device implantation

Possible bridge to transplant - *Likely to be eligible*: defines a patient in whom the transplant evaluation has not been completed, but no contra-indications are anticipated, or in whom a current contra-indication is anticipated to resolve rapidly, such as recent infection.

Possible bridge to transplant - *Moderate likelihood of becoming eligible*: similar to above, but with some potential concerns that might prevent eligibility.

Possible bridge to transplant - *Unlikely to become eligible*: should be used for a patient in whom major concerns have already been identified. These may not have been quantified yet, such as in a patient with known chronic lung disease without recent pulmonary function test measurement, or might be reversible, such as severe renal insufficiency or pulmonary hypertension that might improve after chronic mechanical support. It may be the expectation at the time of implant that the patient will most likely have the assist device as “permanent” or “destination” therapy.

Destination therapy - patient definitely not eligible for transplant.

2 ABBREVIATIONS AND DEFINITIONS

- a. BSA = Body Surface Area
- b. LVEF = Left Ventricular Ejection Fraction
- c. CI = Cardiac Index
- d. LVAS = Left Ventricular Assist System
- e. LVAD = Left Ventricular Assist Device
- f. IABP= Intra-aortic Balloon Pump
- g. IRB
- h. FDA= Food and Drug Administration

3 INTRODUCTION

The HeartMate III LVAS represents the next generation of a mechanical support device. The HeartMate III LVAD is a centrifugal mechanically levitated heart pump designed for both short and long term support in patients afflicted with advanced, refractory left-ventricular heart failure. The purpose of this clinical investigation is to evaluate the safety and effectiveness of the HeartMate III LVAS. This multicenter study is designed to determine if the HeartMate III LVAS provides survival and quality of life benefits that are non-inferior to the HeartMate II LVAS. The trial will enroll patients under one inclusion and exclusion criteria who will be evaluated for a short and long term indication. The trial design also features a pre-defined and powered secondary endpoint to study pump reliability. The study will be conducted in compliance with the Declaration of Helsinki and all IRB and FDA regulatory requirements.

4 MODIFICATION TO THE PROTOCOL

5 STUDY OBJECTIVES AND ENDPOINTS

5.1 Study Objective

The primary objective of this study is to evaluate the safety and effectiveness of the HeartMate III LVAS by demonstrating non-inferiority to the HeartMate II when used for the treatment of advanced, refractory, left-ventricular heart failure.

5.2 Primary Study Endpoints

5.2.1 Short Term Indication

Composite of survival to transplant, recovery or 6 months of LVAD support free of debilitating stroke (Modified Rankin Score > 3) or reoperation to replace the pump.

5.2.2 Long Term Indication

Composite of survival to transplant, recovery or 24 months of LVAD support free of debilitating stroke (Modified Rankin Score > 3) or reoperation to replace the pump.

5.3 Secondary Endpoints

- i. Quality of Life as measured by the EuroQoL-5D-5L (EQ-5D-5L) and Kansas City Cardiomyopathy Questionnaire (KCCQ)
- ii. Functional status as measured by the Six Minute Walk Test (6MWT) and New York Heart Association (NYHA) classification
- iii. Frequency and incidence of pre-defined anticipated adverse events

- iv. Frequency and incidence of device malfunctions
- v. Frequency and incidence of all reoperations
- vi. Frequency and incidence of re-hospitalizations

6 STUDY POPULATION:

- a. Subjects with advanced refractory left ventricular heart failure who meet the following inclusion and exclusion criteria.
- b. Inclusion Criteria
 - i. Subject or legal representative has signed Informed Consent Form (ICF)
 - ii. Age \geq 18 years
 - iii. BSA \geq 1.2 m²
 - iv. NYHA Class III with dyspnea upon mild physical activity, or NYHA Class IV
 - v. LVEF \leq 25%
 - vi. Inotrope dependent OR
CI < 2.2 L/min/m², while not on inotropes and subjects must also meet one of the following:
 - On Optimal Medical management (OMM), based on current heart failure practice guidelines for at least 45 out of the last 60 days and are failing to respond
 - Advanced heart failure for at least 14 days AND dependent on IABP for at least 7 days
 - vii. Females of child bearing age must agree to use adequate contraception
- c. Exclusion Criteria
 - i. Etiology of HF due to or associated with uncorrected thyroid disease, obstructive cardiomyopathy, pericardial disease, amyloidosis or restrictive cardiomyopathy
 - ii. Technical obstacles which pose an inordinately high surgical risk, in the judgment of the investigator
 - iii. Existence of ongoing mechanical circulatory support (MCS) other than IABP
 - iv. Positive pregnancy test if of childbearing potential
 - v. Presence of mechanical aortic cardiac valve that will not be converted to a bioprosthesis or oversewn at the time of LVAD implant
 - vi. History of any organ transplant
 - vii. Platelet count < 100,000 x 10³/L (< 100,000/ml)
 - viii. Psychiatric disease/disorder, irreversible cognitive dysfunction or psychosocial issues that are likely to impair compliance with the study protocol and LVAS management
 - ix. History of confirmed, untreated AAA > 5 cm in diameter within 6 months of enrollment
 - x. Presence of an active, uncontrolled infection
 - xi. Intolerance to anticoagulant or antiplatelet therapies or any other peri/post-operative therapy the investigator will require based upon the patients' health status

- xii. Presence of any one of the following risk factors for indications of severe end organ dysfunction or failure:
 - 1. An INR \geq 2.0 not due to anticoagulation therapy
 - 2. Total bilirubin $>$ 43 $\mu\text{mol/L}$ (2.5 mg/dl), shock liver, or biopsy proven liver cirrhosis
 - 3. History of severe chronic obstructive pulmonary disease (COPD) defined by $\text{FEV}_1/\text{FVC} < 0.7$, or $\text{FEV}_1 < 50\%$ predicted
 - 4. Fixed pulmonary hypertension with a most recent PVR \geq 8 Wood units that is unresponsive to pharmacologic intervention
 - 5. History of stroke within 90 days prior to enrollment, or a history of cerebrovascular disease with significant ($> 80\%$) carotid artery stenosis
 - 6. Serum creatinine \geq 221 $\mu\text{mol/L}$ (2.5 mg/dl) or the need for chronic renal replacement therapy
 - 7. Significant peripheral vascular disease (PVD) accompanied by rest pain or extremity ulceration
- xiii. Patient has moderate to severe aortic insufficiency without plans for correction during pump implant
- xiv. Pre albumin $<$ 150 mg/L, or Albumin $<$ 30g/L (3 g/dL)
- xv. Planned Bi-VAD support prior to enrollment
- xvi. Patient has known hypo or hyper coagulable states such as disseminated intravascular coagulation and heparin induced thrombocytopenia
- xvii. Participation in any other clinical investigation that is likely to confound study results or affect the study
- xviii. Any condition other than HF that could limit survival to less than 24 months

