
Exclusion Criteria
	
 1) Etiology of heart failure (HF) due to or associated with uncorrected thyroid disease, obstructive cardiomyopathy, pericardial disease, amyloidosis or restrictive cardiomyopathy 2) Technical obstacles which pose an inordinately high surgical risk, in the judgment of the investigator 3) Existence of ongoing mechanical circulatory support (MCS) other than IABP 4) Positive pregnancy test if of childbearing potential 5) Presence of mechanical aortic valve that will not be either converted to a bioprosthesis or oversewn at the time of LVAD implant 6) History of any organ transplant 7) Platelet count < 100,000 x 10³/L (< 100,000/ml) 8) Psychiatric disease/disorder, irreversible cognitive dysfunction or psychosocial issues that are likely to impair compliance with the study protocol and LVAS management 9) History of confirmed, untreated AAA > 5 cm in diameter within 6 months of enrollment 10) Presence of an active, uncontrolled infection 11) Intolerance to anticoagulant or antiplatelet therapies or any other peri/post-operative therapy the investigator will require based upon the patients' health status 12) Presence of any one of the following risk factors for indications of severe end organ dysfunction or failure: 
 a) An INR ≥ 2.0 not due to anticoagulation therapy b) Total bilirubin > 43 umol/L (2.5 mg/dl), shock liver, or biopsy proven liver cirrhosis c) History of severe chronic obstructive pulmonary disease (COPD) defined by FEV₁/FVC < 0.7, and FEV₁ < 50% predicted d) Fixed pulmonary hypertension with a most recent PVR ≥ 8 Wood units that is unresponsive to pharmacologic intervention e) History of stroke within 90 days prior to enrollment, or a history of cerebrovascular disease with significant (> 80%) uncorrected carotid stenosis f) Serum creatinine ≥ 221 umol/L (2.5 mg/dl) or the need for chronic renal replacement therapy g) Significant peripheral vascular disease (PVD) accompanied by rest pain or extremity ulceration 13) Patient has moderate to severe aortic insufficiency without plans for correction during pump implant 14) Pre albumin < 150 mg/L (15mg/dL) or Albumin < 30g/L (3 g/dL) (if only one available) ; pre albumin < 150 mg/L (15mg/dL) and Albumin < 30g/L (3 g/dL) (if both available) 15) Planned Bi-VAD support prior to enrollment 16) Patient has known hypo or hyper coagulable states such as disseminated intravascular coagulation and heparin induced thrombocytopenia 17) Participation in any other clinical investigation that is likely to confound study results or affect the study 18) Any condition other than HF that could limit survival to less than 24 months

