12 EXCLUSION CRITERIA

- 1) Etiology of HF due to or associated with uncorrected thyroid disease, obstructive cardiomyopathy, pericardial disease, amyloidosis, or restrictive cardiomyopathy
- 2) Technical obstacles which pose an inordinately high surgical risk, in the judgment of the investigator
- 3) Existence of ongoing mechanical circulatory support (MCS) other than IABP
- 4) Positive pregnancy test if of childbearing potential
- 5) Presence of mechanical aortic cardiac valve that will not be either converted to a bioprosthesis or oversewn at the time of LVAD implant
- 6) History of any organ transplant
- 7) Platelet count $< 100,000 \times 10^3/L$ ($< 100,000/ml$)
- 8) Psychiatric disease/disorder, irreversible cognitive dysfunction or psychosocial issues that are likely to impair compliance with the study protocol and LVAS management
- 9) History of confirmed, untreated Abdominal Aortic Aneurysm (AAA) > 5 cm in diameter within 6 months of enrollment
- 10) Presence of an active, uncontrolled infection
- 11) Intolerance to anticoagulant or antiplatelet therapies or any other peri/post-operative therapy that the investigator will require based upon the patients' health status
- 12) Presence of any one of the following risk factors for indications of severe end organ dysfunction or failure:
 - a) An INR ≥ 2.0 not due to anticoagulation therapy
 - b) Total bilirubin > 43 $\mu\text{mol/L}$ (2.5 mg/dl), shock liver, or biopsy proven liver cirrhosis
 - c) History of severe chronic obstructive pulmonary disease (COPD) defined by $\text{FEV}_1/\text{FVC} < 0.7$, and $\text{FEV}_1 < 50\%$ predicted
 - d) Fixed pulmonary hypertension with a most recent PVR ≥ 8 Wood units that is unresponsive to pharmacologic intervention
 - e) History of stroke within 90 days prior to enrollment, or a history of cerebrovascular disease with significant ($> 80\%$) uncorrected carotid artery stenosis
 - f) Serum Creatinine ≥ 221 $\mu\text{mol/L}$ (2.5 mg/dl) or the need for chronic renal replacement therapy
 - g) Significant peripheral vascular disease (PVD) accompanied by rest pain or extremity ulceration
- 13) Patient has moderate to severe aortic insufficiency without plans for correction during pump implant
- 14) Pre albumin < 150 mg/L (15mg/dL) or Albumin < 30 g/L (3 g/dL) (if only one available); pre albumin < 150 mg/L (15mg/dL) and Albumin < 30 g/L (3 g/dL) (if both available)
- 15) Planned Bi-VAD support prior to enrollment

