8.1 Analysis Population

8.1.1 Intent-to-treat: All Randomized Subjects

This is the primary analysis population for the primary endpoint. Subjects are analyzed under the treatment to which they were randomized.

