8.1.3 As Randomized: All Treated Subjects

This population includes only the Subjects who receive the treatment they were randomized to.

8.1.4 Per Protocol:

As Randomized patients who meet all protocol inclusion and exclusion criteria and are free of major protocol violations. Major protocol violations include:

1. Patients who sign consent after randomization or patients who sign an unapproved consent form
2. Implantation of the VAD using a technique other than sternotomy
3. Missing > 2 pre-specified visits after initial discharge
4. Missing data that may affect the primary outcome:
 - i. Stroke reported but MRS never provided
 - ii. Transplant or explant prior to a study endpoint but the reason for the procedure is not reported

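### The platelet exclusion is printed in units that put the limit at 100 platelets/µL, apparently 1,000-fold too low

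*SAP*

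**What the plan says.** The platelet criterion appears three times: in the protocol synopsis (exclusion 7), in protocol section 12 (item 7) and in the SAP's study population section (6.c.vii). The SAP prints "Platelet count < 100,000 x 10³/L (< 100,000/ml". The two protocol entries carry the same number in the same two units. Nowhere do the documents give the limit per microlitre or as a multiple of 10^9/L, and nothing corrects the line.

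The criterion has a second use. SAP section 8.1.4 defines the Per Protocol set as "As Randomized patients who meet all protocol inclusion and exclusion criteria and are free of major protocol violations", so eligibility as printed in the protocol decides membership of that set. For the intent-to-treat population, SAP section 8.1.1 says: "This is the primary analysis population for the primary endpoint".

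**The concern.** An exclusion limit has to mean what it says in the unit it is printed in. Here the unit places the cut-off at 100 platelets/µL. Read literally, the criterion is close to inoperative: patients with severe thrombocytopenia would not meet it.

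Two things depend on the line. The first is safety at entry. Subjects undergo a surgical implant and must be anticoagulated afterwards (protocol section 17). Laboratory work is done locally (protocol section 16) at up to 70 sites (section 7), so no central laboratory would settle which unit was meant. The second is the Per Protocol set, a further efficacy analysis in a non-inferiority trial. A programmer who checks platelets against the printed limit would flag essentially nobody. One who checks against the presumed limit might remove some subjects. The documents do not say which rule applies.

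**Working it through.** **Inputs.** The two printed forms, 100,000 x 10³/L and 100,000/ml, identical in the synopsis, protocol section 12 and SAP section 6. Conversions: 1 L = 10³ mL = 10⁶ µL.

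**Step 1: do the two forms agree?**
- First form: 100,000 x 10³/L = 10^8/L.
- Second form: 100,000/mL x 1,000 mL/L = 10^8/L.

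They agree exactly. This is not a failed conversion between the two forms.

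**Step 2: what limit is that in customary units?**
- 10^8/L ÷ 10⁶ µL/L = 100/µL.
- 10^8/L ÷ 10^9 = 0.1, that is 0.1 x 10^9/L.

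**Step 3: how far is it from the presumed limit?** Assume that the digits are right and the intended unit is per microlitre.
- 100,000/µL x 10⁶ µL/L = 10^11/L = 100 x 10^9/L.
- Ratio: 10^11 ÷ 10^8 = 1,000.

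For any other intended limit L per µL the factor is L ÷ 100. An intended limit of 50,000/µL, for example, would give a factor of 500. The size of the discrepancy depends on the assumption, but the literal value of 100/µL does not.

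**Step 4: how would it act on individual counts?** The documents give no platelet distribution, so these counts are illustrative only.

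| Count (/µL) | Multiple of printed limit | Excluded as printed? | Excluded at 100,000/µL? |
|---|---|---|---|
| 20,000 | 20,000 ÷ 100 = 200 | No | Yes |
| 50,000 | 50,000 ÷ 100 = 500 | No | Yes |
| 99,000 | 99,000 ÷ 100 = 990 | No | Yes |

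**Step 5: could this be damage from reading the PDF?** That is unlikely, for three reasons.
- Micro units survive in the same lists. The synopsis has "Total bilirubin > 43 umol/L (2.5 mg/dl), shock liver, or biopsy proven liver cirrhosis", and protocol section 12 and the SAP also keep the micro prefix for bilirubin and creatinine.
- A lost micro sign would repair only the second form. The first would become 100,000 x 10³/µL = 10^8/µL, which is 1,000-fold above the presumed limit. Repairing the first form needs a different change, from 10³/L to 10⁶/L.
- Both changes would have to have occurred, in matching fashion, in three separate places.

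**Step 6: are other two-unit criteria sound?** Yes. In protocol section 12, albumin 3 g/dL x 10 dL/L = 30 g/L and pre-albumin 15 mg/dL x 10 dL/L = 150 mg/L, both as printed. Using standard molar masses (584.66 for bilirubin and 113.12 for creatinine, not given in the documents), 2.5 mg/dl converts to 42.8 µmol/L and 221.0 µmol/L, matching the printed 43 and 221. Among the criteria checked, the platelet line is the one with a problem.

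**The case against.** The strongest reply is that this is an editorial slip with little consequence. Sites are selected for LVAD experience (protocol section 31.3), only experienced LVAD staff look after subjects (section 24), and local laboratories must supply their normal ranges (section 29.7). It is hard to imagine such a team converting the printed units and then implanting a patient with 20,000 platelets/µL. Other exclusions overlap: item 11 (intolerance to anticoagulant or antiplatelet therapy), item 12a (raised INR) and item 16 (known coagulation disorders), with item 2 covering surgical risk more generally. Intent-to-treat is primary for the primary endpoint and As Treated for the secondary endpoints. The Per Protocol set changes only if someone was enrolled with a count between 100/µL and the intended limit, and nothing in the documents shows that anyone was. Finally, the intended limit is an inference from general clinical knowledge.

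Most of this stands, and it is why the point is minor. It does not make the line correct: the criterion works only if the reader disregards both printed units.

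A further objection concerns timing. Applying a corrected limit to subjects already enrolled could remove people who satisfied the criterion as written, and in an unblinded trial that choice should not be open once outcomes are known. This stands too, and it affects how the correction should be made.

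**Conclusion.** The concern holds. As printed in all three places, the platelet exclusion is set at 100/µL (0.1 x 10^9/L), a level that would exclude essentially no thrombocytopenic patient. This looks like a unit error in an operative eligibility threshold; no calculation in the plan has failed. If 100,000/µL was intended, the printed limit is too low by a factor of 1,000. That intention is an assumption the sponsor must confirm.

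The importance is low. One of 18 exclusions is affected, the effect on enrolment is probably small, and sample size, power, alpha and the primary intent-to-treat analysis are unaffected. The correction is still worth making because the line bears on safety at entry and on who counts as eligible for the Per Protocol set.

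**What to change.** Ask the sponsor to confirm the intended limit. If it is the presumed one, print < 100 x 10^9/L (< 100,000/µL) in synopsis exclusion 7, protocol section 12 item 7 and SAP 6.c.vii. The protocol must be corrected as well as the SAP, because the Per Protocol definition refers to the protocol's criteria.

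Use the confirmed limit when checking this criterion for the Per Protocol set, and record that decision before outcome data are reviewed. If subjects were enrolled between the printed and confirmed limits, state in advance whether the corrected limit applies to them or only to later enrollees.

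The cost is one line in three places, plus whatever route the sponsor chooses for issuing it: a clarification memo may suffice, or a formal amendment with IRB submission if the change is judged significant under protocol section 28. Sample size, power, alpha and the primary analysis do not change.
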